## STUDY ABSTRACT

- DESIGN:** *A two-arm prospective randomized controlled trial (RCT) in Philadelphia, Houston, and Atlanta. Participants randomized to the control condition will only see the site locator portion of the Get Connected intervention website. It will include information on HIV prevention services. Participants randomized to the intervention condition will receive tailored online content specific to their demographic characteristics (e.g., age, race/ethnicity, location, and relationship status), HIV/STI risk behaviors (e.g., HIV/STI testing history; substance use; communication with partners regarding status) and sociocultural context (e.g., homelessness, incarceration). We will also recruit, enroll, and train 10-15 mystery shoppers per city to conduct a mystery shopper assessment. Two mystery shoppers will visit each testing site separately and complete a standardized assessment of their visit. Site directors from 10 randomly selected testing sites in each city will be interviewed to assess sites' satisfaction with the biannual performance assessments and their improvements in service delivery when working with YMSM.*
- DURATION:** *Mystery shoppers are enrolled for approximately six months, or the time it takes them to complete approximately ten site visits. YMSM participating in the RCT are enrolled for 12 months.*
- SAMPLE SIZE:** *Total study sample size is 480 with the aim of maintaining a randomized sample of approximately 400 online-recruited and retained YMSM for 12 months. After consent, but prior to completion of the baseline survey, YMSM are randomized to either the intervention (n=240) or control (n=240) condition.*
- POPULATION:** *Individuals who were assigned male at birth and currently identify as male. 15-24 year-old (inclusive), self-report as HIV-negative or sero-status unaware, speak and read English, live in Philadelphia, Houston, or Atlanta, and meet one or both of the following high risk criteria: have not received HIV testing in past six months and/or report having consensual anal sex with a man in the past six months.*
- STRATIFICATION:** *Each site (Houston, Atlanta, and Philadelphia) will enroll 160 YMSM and 10-15 mystery shoppers.*

**DATA  
COLLECTION:**

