### 3.0 STUDY DESIGN

#### 3.1 Study Phases

In this four-year study, we will enroll 480 self-reported HIV-negative or sero-status unaware, sexually active YMSM (ages 15-24) across three sites and randomize them into the GC intervention condition or to an attention-control condition. Primary outcomes will include (1) use of HIV prevention services (HIV testing, STI testing) and PrEP awareness and willingness. As secondary outcomes, we will assess PrEP use, sexual risk behaviors, and the linkage and retention in care among newly diagnosed HIV+ cases. We will also examine changes in GC's theorized mechanisms of change, including YMSM's attitudes, norms, self-efficacy, and behavioral intentions to adopt HIV prevention services.

Control condition: Participants randomized to the control condition will have access to the site locator portion of the Get Connected website, which includes information on HIV prevention services. While the provision of a test locator is a form (albeit weak) of an intervention, we felt that withholding referrals to testing and care services would be unethical given YMSM's vulnerability to HIV and STIs. Furthermore, given the availability of search engines to locate HIV/STI testing sites, the test locator condition may be considered usual care. Nevertheless, by providing the testing site locator only, we will be able to test the effect of the GC intervention condition (i.e., user-tailored content focused on HIV/STI testing and PrEP referral and the linkage to high-quality agencies) against the usual care control condition.

Intervention condition: Using a consensus approach to conceptualize health behavior change, the model guiding GC synthesizes The Integrated Behavioral Model and Self-Determination Theory as the theoretical underpinnings of our intervention. These theories emphasize social cognitive factors that impact behavior change and have informed HIV interventions. Consistent with these theories, GC content follows motivational interviewing (MI) principles by focusing on resolving ambivalence about HIV prevention behaviors, increasing self-efficacy for change, and enhancing motivation moving toward action. The intervention was developed by customizing content based on YMSM's psychosocial and sexual

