### 3.2 Study Population

For the primary objective, we plan to recruit a diverse sample of 15-24 year olds. Of the 480 participants, we propose that 98 (20%) will be non-Hispanic white men, 232 (48%) will be non-Hispanic black men, 122 (25%) will be Latino men, 22 (5%) will be non-Hispanic Asian-Pacific Islanders, and 6 (2%) will be other non-Hispanic or multi-racial men. Transgender participants are excluded in this protocol as the intervention has not been adapted to meet the needs of transgender youth.

Eligibility criteria will include the following: Individuals who were assigned male at birth and currently identify as male, 15-24 years old (inclusive), self-report as HIV-negative or sero-status unaware, speak and read English, live in Philadelphia, Houston, or Atlanta, and meet one or both of the following high risk criteria: have not received HIV testing in past six months and/or report having consensual anal sex with a man in the past six months.

For the secondary objective, we plan to recruit a diverse group of 10-15 mystery shoppers per city. Mystery shoppers will be 18 to 24 years old (inclusive).

Eligibility criteria will include the following: Individuals who were assigned male at birth and currently identify as male, 18-24 years old (inclusive) at time of screening, self-report as HIV-negative, speak and read English, live in Philadelphia, Houston, or Atlanta, are able to travel to and from HIV/STI testing sites, report same-sex attraction, and have access to internet via a computer or smartphone.

For the tertiary objective, we will randomly select 10 testing sites per city who participated in the mystery shopper perspective and conduct a semi-structured qualitative in-depth interview with the site's director.

Eligibility criteria will include the following: Individuals who are site directors of an HIV/STI testing site in Philadelphia, Atlanta, or Houston, and who can speak and read English.

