## 4.0 ELIGIBILITY AND SCREENING

### 4.1 Primary Objective (RCT): Inclusion Criteria

- *Assigned male sex at birth and currently identifies as male*

- *Aged 15 to 24 years (inclusive) at time of screening*
- *Self-report as HIV-negative or sero-status unaware*
- *Speak and read English*
- *Not be on PrEP at time of enrollment*
- *Report having consensual anal sex with a male partner in the prior 6 months and/or report having not received HIV testing in prior 6 months*
- *Reside in Philadelphia, Houston, or Atlanta*
- *Access to internet*

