#### **4.3 Secondary Objective (Mystery Shoppers): Inclusion Criteria**

- *Assigned male sex at birth and currently identifies as male*
- *Aged 18 to 24 years (inclusive) at time of screening*
- *Self-report as HIV-negative*
- *Speak and read English*
- *Report same sex attraction*
- *Reside in Philadelphia, Houston, or Atlanta*
- *Able to travel to and from HIV/STI testing sites*
- *Access to internet via a computer or smartphone*

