## **4.9 Screening**

### Primary objective: Web-based recruitment screener:

Participants who click on the banner advertisements will be taken to an online screening survey, hosted on SurveyGizmo.com, which will include the eligibility script and questions from the RCT Participant Eligibility Screener. For those who meet eligibility criteria, we will ask for a first name, email address, and phone number. For those who do not meet eligibility criteria, there will be an option to provide a first name and email address if they want to be contacted about future studies. Those individuals who initially screened ineligible because they did not report having anal sex with a man in the past 6 months will be re-contacted to take the online screener again. Web-based screening instruments allow for real-time data collection across multiple outreach modes (e.g., banner ads, flyers, in-person outreach) pooled into a single stream. We will use Secure Socket Layer (SSL) encryption for transfers of information online and data will be stored in the secure, HIPAA-compliant servers of SurveyGizmo. The Emory AC team maintains a business partner HIPAA agreement with SurveyGizmo.

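### The RCT eligibility list never requires sex with, or attraction to, men: no HIV test in six months is enough, so a man who is not a YMSM can qualify

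*Combined protocol and SAP*

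**What the plan says.** Section 4.1 states the RCT risk criterion in two limbs: recent consensual anal sex with a male partner, "and/or report having not received HIV testing in prior 6 months". Section 3.2 confirms that either limb is enough: participants must "meet one or both of the following high risk criteria". The Abstract uses the same two limbs: "have not received HIV testing in past six months and/or report having consensual anal sex with a man in the past six months".

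The other inclusion criteria in 4.1 cover sex at birth and gender identity, age, self-reported HIV status, English, not being on PrEP, city of residence and internet access. The nine exclusions in 4.2 cover sex at birth, gender identity, age, HIV status, English, PrEP, residence, incarceration and plans to move. None of them concerns partners, sexual activity or attraction.

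Section 3.1 describes those to be enrolled as "sexually active YMSM (ages 15-24" and the list of abbreviations expands YMSM as young men who have sex with men. The primary objective (2.1) and the hypotheses (2.4) are about YMSM. For mystery shoppers, section 4.3 has a separate line, "Report same sex attraction", and section 4.4 excludes those who do not.

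Section 4.9 says that people who "initially screened ineligible because they did not report having anal sex with a man in the past 6 months" will be asked to take the screener again.

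**The concern.** Sites enrol against listed criteria, not against the label used for the population. The only reference to sex with men in the RCT list is one half of an either/or. The other half, not having tested recently, can be true of any young man, including one with no male partners and no attraction to men. The shopper list shows that the sponsor wrote an explicit requirement where it wanted one.

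Two things are at stake. The first is who the result applies to: the objective concerns YMSM, while the written rule defines a wider group. The second is dilution. Men with little reason to test for HIV or consider PrEP would probably show little effect of the intervention. Section 2.4 specifies intention-to-treat with all randomised participants included, so they could not simply be dropped at analysis.

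The recruitment plan in section 4.7 leaves room for this. It uses targeted advertisements on general social media, and referral chains especially for ages 15 to 17. The socio-sexual networking sites, which would act as a filter, are limited to those aged 18 and over.

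**Working it through.** **1. Criterion check.** Take the four combinations of the two limbs in 4.1, for a man who meets every other criterion.

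| Anal sex with a man, prior 6 months | HIV test, prior 6 months | Eligible under 4.1, 3.2 and the Abstract |
|---|---|---|
| Yes | No | Yes |
| Yes | Yes | Yes |
| No | No | **Yes** |
| No | Yes | No |

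The third row is the gap. It includes YMSM with no recent anal sex, whom a testing trial may well want. It also includes men who are not YMSM at all, and nothing in 4.1 or 4.2 separates the two.

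**2. Section 4.9 against the same table.** Lack of recent anal sex makes a man ineligible only in the fourth row, where he has also tested recently. That group exists, so the re-contact rule can operate. What it leaves out is that a fourth-row man also becomes eligible once his last test is more than six months old.

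**3. The plan's sample size, for context.** Section 10.2 gives 80% power, two-sided 0.05, at least 400 participants and a 13-point difference, but no control rate. Allocation is 1:1 (section 5.3). The standard formula per arm, with p̄ the mean of p1 and p2, is

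n = [1.96√(2p̄(1−p̄)) + 0.842√(p1(1−p1) + p2(1−p2))]² / (p2−p1)²

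- Control 25%: 200 per arm, total 400, which matches the plan.
- Control 30%: total 430.
- Control 50%: total 456.
- Control 60%: total 412.

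A 25% control rate is therefore an assumption that reproduces the plan's figure. It is not a value the plan states.

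**4. Illustrative dilution.** Let f be the share of enrolled men who are not YMSM, with no intervention effect in them. With 200 per arm,

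power = Φ{[(p2−p1)√200 − 1.96√(2p̄(1−p̄))] / √(p1(1−p1) + p2(1−p2))}

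At f = 0 the rates are 25% and 38%: (1.838 − 1.288)/0.650 = 0.847, so power is 80%.

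Two versions bracket the result for f > 0:

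- *Control rate held at 25%*, so the non-YMSM test as often as control YMSM. The difference becomes 13 × (1−f) points.
- *Non-YMSM never meet the endpoint in either arm.* Both rates are multiplied by (1−f).

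| f | Rates, first version | Power | Rates, second version | Power |
|---|---|---|---|---|
| 5% | 25.0% v 37.35% | 76% | 23.75% v 36.1% | 77% |
| 10% | 25.0% v 36.7% | 72% | 22.5% v 34.2% | 74% |

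The documents give no value for f.

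**The case against.** The strongest reply has four parts.

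- **The either-limb rule is deliberate.** It appears in three places, and a testing trial has good reason to admit untested YMSM who have had no recent anal sex. This stands: the rule should stay, and the gap is only that YMSM status is presumed instead of listed.
- **The target population is named throughout.** Sections 2.1, 3.1, 3.3, 3.4 and 4.7 all speak of YMSM. This shows the intention, but an intention is not a criterion that staff can apply.
- **Practical filters exist.** There is a separate eligibility screener, some recruitment comes from socio-sexual networking sites, and every participant attends an in-person enrolment visit. The screener's questions are not in the text and may ask about sex with men. So actual enrolment of men outside the population is unproven, and a large share is less likely than the bare criteria suggest. None of these steps is required by the protocol to establish YMSM status.
- **The power figures rest on assumed inputs.** This is correct, and it is why they are shown only as illustration.

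A reader might also infer that the re-contact rule in section 4.9 contradicts the either-limb criterion, because it names only anal sex as the reason for ineligibility. The documents do not support that. Men who fail both limbs are ineligible, and lack of recent anal sex is part of the reason, so the rule is consistent with 4.1. It is incompletely worded.

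**Conclusion.** The gap is definite on the face of the text. Under the Abstract and sections 3.2 and 4.1, not having tested in six months satisfies the risk criterion alone, and no other criterion requires sex with, or attraction to, men. The written rule therefore describes a wider population than the sexually active YMSM of section 3.1 and the objective in 2.1.

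The size of the consequence is unknown. If non-YMSM were 5% of the sample, power would be roughly 76–77% instead of 80%; at 10%, roughly 72–74%. Both ranges assume a 25% control rate, 200 analysed per arm, a 13-point effect in YMSM and no effect in others. It would go too far to conclude that the trial will be underpowered for this reason, or that such men will enrol in number, since the documents give neither the share nor the control rate. Nor is the comparison between arms biased, because randomisation protects it. The problem is applicability and possible dilution. It should be corrected because the defect is clear and the correction is small.

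**What to change.** - Add a stand-alone YMSM criterion to section 4.1, section 3.2 and the Abstract, with a matching screener item. It must be met before the either-limb risk criterion is considered, and that criterion can stay as it is.
- Decide what defines a YMSM for this trial, sex with men (with any look-back period) or attraction to men, and make section 3.1 agree. Borrowing the shoppers' attraction wording alone would still admit men who are not sexually active, so 3.1 would then have to change in meaning. If sexual activity is intended, the criterion must say so.
- If the screener already asks about sex with or attraction to men, state that in the protocol and list it as a criterion.
- In section 4.9, say that re-contact applies to men who failed both limbs, that is, no recent anal sex with a man and an HIV test in the prior six months.

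The cost is one criterion, one screener item and aligned wording in the Abstract and three sections (3.1, 3.2, 4.1), plus a phrase in 4.9. The downside is the loss of some candidates who would otherwise screen in. That loss should be small, although the documents give no figure, and those men are outside the target population.

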#### **4.2 Primary Objective (RCT): Exclusion Criteria**

- *Assigned female sex at birth*
- *Assigned male sex at birth but does not currently identify as male*
- *Aged 14 years or younger or 25 years or older at time of screening*
- *HIV-positive*
- *Does not speak or read English*
- *Currently taking PrEP*
- *Does not reside in Philadelphia, Houston, or Atlanta*
- *Currently incarcerated*
- *Planning to move out of the region in next 12 months*

#### **4.3 Secondary Objective (Mystery Shoppers): Inclusion Criteria**

- *Assigned male sex at birth and currently identifies as male*
- *Aged 18 to 24 years (inclusive) at time of screening*
- *Self-report as HIV-negative*
- *Speak and read English*
- *Report same sex attraction*
- *Reside in Philadelphia, Houston, or Atlanta*
- *Able to travel to and from HIV/STI testing sites*
- *Access to internet via a computer or smartphone*

#### **4.4 Secondary Objective (Mystery Shoppers): Exclusion Criteria**

- *Assigned female sex at birth*
- *Assigned male sex at birth but identifies as transgender or gender non-conforming*
- *Aged 17 years or younger or 25 years or older at time of screening*
- *HIV-positive*
- *Does not speak or read English*
- *Does not report same sex attraction*
- *Does not reside in Philadelphia, Houston, or Atlanta*
- *Currently incarcerated*
- *Planning to move out of the region in next 12 months*
- *Unable to travel to and from HIV/STI testing sites*
- *Does not have access to internet via a computer or smartphone*

#### **4.5 Tertiary Objective (Site Directors): Inclusion Criteria**

- *Speak and read English*
- *Site director of an HIV/STI testing site in Philadelphia, Atlanta, or Houston*

#### **4.6 Tertiary Objective (Site Directors): Exclusion Criteria**

- *Does not speak and read English*
- *Is not a site director of an HIV/STI testing site in Philadelphia, Atlanta, or Houston*

#### **4.7 Recruitment**

For the primary objective, we will use geographically targeted ads on a range of social media outlets. We will work closely with the U19 Management and Technology Cores for guidance on recruitment, including use of the Technology Core's bank of recruitment images. We will also recruit from socio-sexual networking sites (e.g., Grindr, BBRT) for YMSM who are 18 years or older. Promotional materials will describe the study and provide a link to the SurveyGizmo Participant Eligibility Screener (see Section 4.0 for eligibility criteria). Once determined eligible, YMSM will be contacted to schedule their baseline visit at the SRV. We will also follow respondent-driven sampling (RDS) methods and use a long-chain referral method to supplement recruitment, especially with the adolescents (15-17) who may be harder to reach than young adults (18-24).

For the secondary objective, we will use geographically targeted ads on a range of social media outlets. We will also work closely with the ATN site in each city to recruit in community spaces. If an individual is interested in being a mystery shopper, they will complete a Qualtrics screening survey to determine their eligibility. If they are eligible, the study team will contact them for an interview.

For the tertiary objective, we will randomly select 10 directors of HIV testing clinics in each city. To be included in the sample for randomization, the site must have been visited and assessed by participants in the GC study. If a site is selected, the study team will contact the site or the site director (if contact information is available) to schedule an interview.

#### **4.8 Informed Consent**

For the primary and secondary objectives, the informed consent process will occur on the day the enrollment visit is held. Interested persons will arrive to the SRV location, where they will be guided through the informed consent process by study staff, who will explain all study procedures and answer questions concerning the study and consent process. The research staff member will give the participant as much time as needed and will address any questions or concerns they may have. The research staff member will ask the participant questions to gauge comprehension. The consent/assent form describes all study procedures, including confidentiality and privacy, information about potential risks, discomforts, benefits of participation, and information regarding

who they can contact with further questions. It also states that participation is voluntary, that participants may decide not to take part or to withdraw from the study at any time without penalty or loss of any benefit to which they might otherwise be entitled. Participants can refuse to answer any question, and can withdraw from the study at any time. The PIs, Co-PIs, or designee at each site will review all informed consents and assents.

**Assessing for decisional capacity.** For all participants, the study staff reviews the informed consent/assent to make an assessment of the youth's decisional capacity and ability to provide consent/assent prior to signing, using a 2-step process. First, the study staff determines if the person understands the study goals by asking "Can you tell me what this study is about?" In step 2, potential participants will be asked questions designed to assess their capacity to understand, appreciate, reason with, and express a choice about participation in our specific protocol. Participants will be asked to: name things they will be expected to do during the study; explain what they would do if they no longer wished to participate in the study; explain what they would do if they experienced distress during the study; and identify potential risks for participating in the study. For youth who cannot answer these questions, the study staff will go back and review the relevant elements of consent with the participant again and repeat the process. Youth who appear not to understand after repeated review will not be enrolled in the study.

**Waiver of parental consent.** We will request that the UNC-CH IRB as the central/single IRB (IRB of Record) grant a waiver of parental consent to participate in this research study for youth participants who are 15 to 17 years of age. The research team has been granted waivers of parental permission for prior studies with sexual minority youth. Under 45 CFR 46.408 (c), an IRB has the authority to waive parental permission if it determines that "a research protocol is designed for conditions or a subject population for which parental or guardian permission is not a reasonable requirement to protect the subjects" and "an appropriate mechanism for protecting the children who will participate as research subjects is substituted" and "that the waiver is not inconsistent with Federal, State, or local law." A waiver of parental/legal guardian permission will be sought given that minor individuals can often seek sexually transmitted infection (STI) and HIV testing without parental/legal guardian permission, depending on each site's state laws. Requiring parental permission may place participants at risk for outing themselves as part of the LGBT community or being at risk for HIV infection. A waiver of parental permission for studies with LGBT youth that do not involve greater than minimal risk is a common practice among researchers working in the area of gay and lesbian health/mental health. This is done to avoid the selection biases operating in only recruiting youth whose parents are both aware of and comfortable with their sexual orientation. Commonly, these youth have explored their sexual orientation without their parents' knowledge as the youth struggle with issues of disclosure and its consequences within the social, religious, and economic context of their families. A requirement for parental permission in this type of study could not only affect a person's willingness to participate, but could also potentially impact the ability of researchers to engage in this type of research with sexual minority youth.

If the purpose of requiring parental permission as stated in CFR is to protect the minor subject, then requiring parental permission for youth in these circumstances is not a reasonable requirement. Additional privacy protections are provided in that all assessments, notes, reports, and other records will be identified by only a coded number to maintain participant confidentiality. These records and any forms that do contain identifying information (e.g., consent/assent forms, contact information) will be kept in a locked, limited access area (such as a locked file cabinet) at the participating site.

For the tertiary objective, any randomly selected site director who is eligible, willing, and capable of being interviewed will be consented over BlueJeans and will be offered a copy of the consent form.

